### 3.1.2 Sample Size

The sample size was estimated based on the following assumptions:

Design parameters:

One-sided Type I Error=0.05

Multiple comparison method= Hochberg's step up

Rejection region=Right tail

Treatment parameters:

Arm	Mean volume percentage	Standard deviation	Sample size per group
22G	67	15.29	25
19G	77	4.67	25
19GFlex	77	4.67	50

Overall power:

Global (reject any  $H_{0i}$ ): 0.912

Conjunctive (reject all  $H_{0i}$ ): 0.901

Given the above assumptions, a total sample of 100 subjects will be required where 50 subjects will be in 19 G Flex arm, and 25 subjects in the 19 G and 22 G arms respectively.

### 3.1.3 Statistical Methods

Two-sample  $t$ -test statistic will be computed as follows.

$$T_i = \frac{\bar{x}_i - \bar{x}_0}{s_{\bar{x}_i - \bar{x}_0}}, \text{ for } i=1, 2;$$

where  $\bar{x}_0$  is mean volume percentage of 22 G Arm,

$\bar{x}_1$  is mean volume percentage of 19 G Flex Arm,

$\bar{x}_2$  is mean volume percentage of 19 G Arm,

$$s_{\bar{x}_i - \bar{x}_0} = \sqrt{\frac{s_i^2}{n_i} + \frac{s_0^2}{n_0}},$$

$n_0$  is sample size of 22 G Arm,

$n_1$  is sample size of 19 G Flex Arm,

$n_2$  is sample size of 19 G Arm.

Now, for each null hypothesis p-value will be computed using one-sided right tail test with type-1 error=0.05 using the following:

$$p_i = P(T_i > t_i) = 1 - \Phi(t_i)$$

where  $T_i$  follows standard normal distribution and  $\Phi(\cdot)$  is cumulative distribution function.

Next, let  $p_{(1)} < p_{(2)}$  be the ordered p-values and  $H_{(1)}, H_{(2)}$  be the associated null hypotheses. The Hochberg step up procedure will be carried out as following:

- Step 1: If  $p_{(2)} > \alpha$  retain  $H_{(2)}$ , otherwise reject all hypotheses and stop.
- Step 2: If  $p_{(1)} > \alpha/(3-1)$  retain  $H_{(1)}$  and stop; otherwise reject  $H_{(1)}$  and stop.

The adjusted p-values for individual hypotheses will be computed by:

$$\tilde{p}_i = \begin{cases} p_{(i)} & \text{if } i = 2 \\ \min(\tilde{p}_{(i+1)}, 2p_{(i)}) & \text{for } i = 1 \end{cases}$$

The adjusted p-value for the global hypothesis will be computed using the following:

$$\tilde{p} = \min(\tilde{p}_1, \tilde{p}_2)$$

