8.2.4. Randomization

Enrolled patients will be assigned to the 19G Flex, 22 G or 19 G Arm in a 2:1:1 ratio by randomization schedules which will be computer-generated using a pseudo-random number generator. An Interactive Web Response System (IWRS) will be utilized.

Randomization will be stratified (block randomization) by the following strata:

- Investigational center
- PCL location: head/uncinate, other

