9.1. Study Hypothesis and Sample Size Calculation

Sample size was calculated based on assumptions for the primary endpoint as well as for secondary endpoint c):

9.1.1. *Primary endpoint considerations:*

The study hypothesis states that for either of the 19 G Flex and 19 G Arms, the volume of actual aspirated cyst fluid as a ratio (%) of estimated maximal volume is superior by at least 10% compared to that of the 22 G Arm.

The study investigators provided the following experience-based estimate of the primary endpoint (aspirate volume as % of max volume based on EUS image of the cyst):

Figure 4 – Hypothesis Generating References (Primary Endpoint)

Site Investigator	Mean Volume Ratio (%) for 19G and 19Flex needles	Mean Volume Ratio (%) for 22G needles
Investigator 1	80%	50%
Investigator 2	90%	70%
Investigator 3	90% Unilocular cysts, 50% Multi-locular	80%

	cysts, 80% Blended mean	
Investigator 4	90%	90%
Investigator 5	90%	50%
Investigator 6	85%	65%

From the above table, bootstrap method with 10,000 resamples yielded an estimated mean of 67.44% and standard deviation of 15.29% for 22G, and a mean of 85.9% and standard deviation of 4.67% for 19G/19G Flex.

The assumption was made that the mean of the “control group”, namely the 22G arm, will be 67% with a standard deviation of 15.29%.

Two null hypotheses are made:

- H_{01} : Mean volume ratio of 19 G Flex Arm and 22 G Arm are the same
- H_{02} : Mean volume ratio of 19 G Arm and 22 G Arm are the same

The alternative hypothesis is:

- H_1 : Mean volume ratio of 19 G Flex/19G Arm is superior to 22 G Arm

If 50 patients are enrolled in the 19 G Flex Arm and 25 patients each in the 19 G and 22 G Arm, the study will have 90% conjunctive power to detect the rejection of both null hypotheses to demonstrate superiority of the mean volume ratio of 19 G Flex Arm and 19 G Arm to that of 22 G Arm by 10% or more. Thus, a minimum of 100 patients (50+25+25=100) are required.

9.1.2. Secondary endpoint c) considerations:

The study hypothesis states that the EUS-FNA 19 G Flex needle is superior to the EUS-FNA 22 G standard and 19 G standard needles in the secondary endpoint c) measure, which requires access or adequate aspirate volume for two standard assays expected from successful EUS-FNA procedures in PCL assessment indications.

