### 3.2.3 Statistical Methods

Test statistics  $T_i$  with pooled variance will be computed as follows.

$$T_i = \frac{\hat{\pi}_2 - \hat{\pi}_i}{\sqrt{\hat{\pi}_i(1 - \hat{\pi}_i)\left(\frac{1}{n_i} + \frac{1}{n_2}\right)}}, \quad i = 0, 1$$

where  $\hat{\pi}_2$  is the sample proportion for 19G Flex arm,

$\hat{\pi}_i$  are the sample proportions for 19G arm and for 22G arm, and

$$\hat{\pi}_i = \frac{n_2 \hat{\pi}_2 + n_i \hat{\pi}_i}{n_2 + n_i}.$$

Now, for each null hypothesis p-value will be computed using one-sided right tail test with type-1 error=0.05 using the following:

$$p_i = P(T_i > t_i) = 1 - \Phi(t_i)$$

where  $T_i$  follows standard normal distribution and  $\Phi(\cdot)$  is cumulative distribution function.

Next let  $p_{(1)} < p_{(2)}$  be the ordered p-values and  $H_{(1)}, H_{(2)}$  be the associated null hypotheses. The Hochberg step up procedure will be carried out as following:

- Step 1: If  $p_{(2)} > \alpha$  retain  $H_{(2)}$ , otherwise reject all the null hypotheses and stop.

- Step 2: If  $p_{(1)} > \alpha / (3 - 1)$  retain  $H_{(1)}$  and stop; otherwise reject  $H_{(1)}$  and stop.

The adjusted p-values for individual hypotheses will be computed by:

$$\tilde{p}_i = \begin{cases} p_{(i)} & \text{if } i = 2 \\ \min(\tilde{p}_{(i+1)}, 2p_{(i)}) & \text{for } i = 1 \end{cases}$$

The adjusted p-value for the global hypothesis will be computed using the following:

$$\tilde{p} = \min(\tilde{p}_1, \tilde{p}_2)$$

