#### **4.5 Control of Systematic Error**

Stratified randomization of needle types (with PCL Location strata) will be done to control for selection bias.

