## 5.4 Justification of Pooling

Poolability of subjects from study sites will be based on the fact that each site follows the identical clinical protocol. At the end of the study, to justify pooling data across sites, the

Boston Scientific

Statistical Analysis Plan - Randomized Evaluation of PCLs Using Three EUS-FNA Needles

90912872 Rev/Ver AA

Page 21 of 24

comparability of baseline variables and demographic characteristics will be assessed across sites. Baseline demographic characteristics include age and gender. Also, the effect of study site will be investigated to determine the poolability of primary endpoint from different sites. If low enrolling sites exist (fewer than 5 subjects per site for example), they may be combined into one 'center' for purposes of poolability analysis. An analysis of variance will be used for the primary endpoint to assess differences between study centers. Each test will be done at a 5% significance level, with no adjustment for multiplicity of variables. If a significant difference is found among centers, then multiple comparisons of centers will be done with an overall significance level of at most 5%, to identify any sites significantly different from the rest. Subsequently, at the end of the study, the primary endpoint will be analyzed both with and without these sites.

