## 5.5 Multivariable Analyses

Multivariate analyses will be carried out to assess potential correlations between the primary endpoint and PCL location, PCL size, route of access (duodenal, esophageal or gastric), needle used, and number of locules. To analyze the salvage cross-over rate, the mixed model multivariate analysis approach above or any other suitable analysis approach will be adopted. Other multivariate analysis (e.g. impact of different predictors to salvage or not) will be done (if necessary) to address any clinical need.

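### Randomisation is stratified by centre and cyst location, but both confirmatory tests ignore the strata and SAP 4.5 names only location

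*SAP*

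**What the plan says.** Protocol 8.2.4 states: "Randomization will be stratified (block randomization) by the following strata". It lists two: "Investigational center", and PCL location in two levels (head/uncinate, other). With 7 to 12 centres this gives 14 to 24 strata.

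SAP 4.5 describes the same scheme with one factor: "Stratified randomization of needle types (with PCL Location strata) will be done to control for selection bias". Centre is not mentioned.

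Neither confirmatory test contains a stratum term:

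- **Primary (SAP 3.1.3).** A two-sample t "test statistic will be computed as follows": a difference of two arm means over an unpooled standard error, referred to the standard normal.
- **Endpoint c (SAP 3.2.3).** A two-proportion z statistic "with pooled variance will be computed as follows".

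Each endpoint applies Hochberg's procedure to its two comparisons at one-sided 0.05.

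The strata appear only in supporting work, and only for the primary endpoint. SAP 5.5 says: "Multivariate analyses will be carried out to assess potential correlations between the primary endpoint and PCL location, PCL size, route of access"; centre is not in its list. SAP 5.4 looks at centre for poolability: "An analysis of variance will be used for the primary endpoint to assess differences between study centers".

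**The concern.** Stratified blocks force the arms to be nearly balanced on centre and location. If those factors affect the outcome, balancing removes their contribution from the real sampling variability of the arm difference. The unadjusted standard error still counts it. The test statistic is then divided by too large a number, and the test rejects less often than its nominal level under the null.

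What is at stake is efficiency and consistency, not validity. The confirmatory standard errors do not match the way patients were allocated, and power may be lost on data already collected. Endpoint c has the least room: it sets the sample size and is planned at a conjunctive power of only 0.808. A reader of SAP 4.5 alone would also get an incomplete account of the randomisation.

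**Working it through.** **1. Reproduce the planned powers.** Inputs are from SAP 3.1.2 and 3.2.2: means 67/77/77, SDs 15.29/4.67/4.67 and n = 25/25/50 (22G/19G/Flex); rates 0.91/0.75/0.75 and n = 121/61/61 (Flex/19G/22G). Simulating the unstratified tests with Hochberg gives these conjunctive/global powers:

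- Primary: 0.906/0.917 with a Welch t reference and 0.915/0.927 with the SAP's normal reference; stated 0.901/0.912.
- Endpoint c: 0.805/0.947; stated 0.808/0.947.

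The planned powers therefore come from unstratified tests, and they reproduce.

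**2. Approximate size.** Let strata explain a share r of the variance in every arm, with perfect balance. The true variance of the difference is (1 - r) times what the unadjusted formula estimates, so size is about 1 - Φ(1.645/√(1 - r)).

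- r = 0.10: 1.645/0.949 = 1.734, size 0.041
- r = 0.20: 1.645/0.894 = 1.839, size 0.033
- r = 0.30: 1.645/0.837 = 1.966, size 0.025

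Incomplete blocks make the balance imperfect, so simulated sizes should be a little higher.

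**3. Primary endpoint, simulated.** N = 243 at 2:1:1, 10-point effect. Assumed, not in the documents: 10 centres x 2 locations, blocks of 4, 40% head/uncinate, unequal centre sizes. There were 8,000 runs per case (6,000 for SD 25). Unadjusted is the SAP statistic. Adjusted is a linear model on arm, centre and location with HC3 variances and a t reference.

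| Case | Unadjusted size | Conjunctive power, unadjusted to adjusted |
|---|---|---|
| Planned SDs, no centre effect | 0.054 | 0.999 to 0.999 |
| SD 15.29 in all arms (assumed), centre 10% | 0.046 | 0.978 to 0.979 |
| Same, centre 20% | 0.036 | 0.984 to 0.988 |
| Same, centre 30% | 0.028 | 0.988 to 0.995 |
| Within-centre SD 20 (assumed), centre SD 15.29 shared by all arms | 0.026 | 0.71 to 0.82 |
| Within-centre SD 20, centre means by arm as in Figure 4, 12 centres | 0.050 | 0.73 to 0.74 |
| SD 15.29, no centre effect | not tabulated | 0.970 to 0.966 |
| SD 25 (assumed), no centre effect | not tabulated | 0.64 to 0.62 |

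A separate simulation (45% head/uncinate, 7 to 12 centres) gave sizes of 0.039-0.046 at 10% and 0.034-0.036 at 20%. With a true difference of 6 points instead of 10, so that power is away from its ceiling, conjunctive power went from 0.634 to 0.667 at 10% and from 0.660 to 0.728 at 20%.

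The normal reference in SAP 3.1.3 pulls slightly the other way: P(T > 1.645) is 0.056 at 26 df and 0.052 at 65 df.

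**4. What Figure 4 supports.** Protocol 9.1.1 reports a "standard deviation of 15.29% for 22G, and a mean of 85.9% and standard deviation of 4.67% for 19G/19G Flex". By investigator, 19G/Flex minus 22G is 30, 20, 0, 0, 40 and 20. The 22G values run from 50 to 90, the 19G/Flex values only from 80 to 90, and the two columns correlate at about 0.16. A centre effect is plausible, but the spread sits almost entirely in 22G. That is the case in which adjustment gains little.

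**5. Endpoint c, simulated.** Rates 0.91 against 0.75; the centre effect is an assumed SD on the logit scale. Sizes are from the second run.

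| Centre logit SD | Size, unadjusted / CMH | Conjunctive power, unadjusted to CMH | Same, second run |
|---|---|---|---|
| 0 | 0.050 / 0.049 | 0.793 to 0.790 | 0.798 to 0.791 |
| 0.5 | 0.048 / 0.051 | 0.797 to 0.799 | 0.790 to 0.790 |
| 1.0 | 0.041 / 0.051 | 0.813 to 0.831 | 0.806 to 0.823 |
| 1.5 | 0.037 / 0.053 | 0.817 to 0.860 | 0.814 to 0.851 |

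**6. An adjustment that would do harm.** An ordinary equal-variance model at 121/61/61 with the planned SDs pools to (182 x 21.81 + 61 x 233.78)/243 = 75.0.

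- Flex against 22G: model SE √(75.0(1/121 + 1/61)) = 1.36; true SE √(21.81/121 + 233.78/61) = 2.00. Size = 1 - Φ(1.645 x 1.36/2.00) = 0.13.
- 19G against 22G: model SE √(75.0 x 2/61) = 1.57; true SE √(255.59/61) = 2.05. Size = 0.10.

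Simulation agrees: 0.129 and 0.104, against 0.051 and 0.050 with HC3.

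**The case against.** The unadjusted tests are valid. The planned powers reproduce with them, and under the planned SDs the primary endpoint needs 100 patients while the trial enrols 250. Figure 4, the only evidence in the documents on centre differences for this endpoint, points to a case with almost no gain. The 0.71-to-0.82 result is constructed: it takes the spread of 22G opinions as a centre effect in every arm and adds an assumed within-centre SD of 20 where 4.67 is planned for 19G/Flex, so that centre explains 15.29²/(15.29² + 20²) = 37% of variance. SAP 5.4 and 5.5 already examine centre and location, and SAP 5.5 mentions a mixed model. The gap in SAP 4.5 is an incomplete parenthesis in a plan that is based on the protocol.

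Much of this stands. It limits the size of the point, and the largest case should be read as an upper illustration. It does not remove the point. The supporting analyses leave both hypothesis tests unchanged, and none of them gives endpoint c a stratified test. SAP 5.5 brings in the mixed model for the salvage cross-over rate.

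One objection concerns the remedy: a CMH p-value reported with a Mantel-Haenszel risk difference can occasionally disagree with that estimate's interval. The combination is acceptable if the SAP states which one decides.

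**Conclusion.** The concern holds. Randomisation uses centre and location, both confirmatory tests ignore them, and SAP 4.5 omits centre. The tests are mildly conservative if the strata are prognostic in all arms, and more than mildly so only when strata explain about 30% of variance or more. Type I error is not inflated, and planned power is not overstated for this reason.

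For the primary endpoint the loss is nil under the planned SDs with no centre effect, and under 1 point at a common SD of 15.29. It becomes material only if patient-level variation exceeds the plan, or the true effect is smaller, and centre effects are shared across arms. For endpoint c, adjustment changes power by -0.3 to +4.3 points as the centre logit SD goes from 0 to 1.5.

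The number and size of centres, the block size, the location mix and the centre effects are all assumptions. This is a recommended change, held with medium confidence about how much it would matter.

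**What to change.** 1. **Primary endpoint.** Fit a linear model with arm, centre and PCL location as additive terms, because 14 to 24 strata are too many for full cross-classification. Use HC3 or arm-specific variances and pass the one-sided t-based p-values into the existing Hochberg steps. Do not use a common-variance model.
2. **Endpoint c.** Take the p-value from a Cochran-Mantel-Haenszel test stratified by centre and location, and report the Mantel-Haenszel risk difference as the estimate. State that the CMH p-value decides. A Wald test on that risk difference is a poor substitute: its power is 0.746 against 0.793 for the plan's z when centre has no effect.
3. **Small centres.** Prespecify one combining rule, as in SAP 5.4, for both endpoints.
4. **Sensitivity.** Keep the unadjusted tests of SAP 3.1.3 and 3.2.3.
5. **SAP 4.5.** Name both strata.

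A separable matter: the SAP 5.4 comparison of overall centre means does not show whether the needle effect varies by site. A site-by-arm interaction test or forest plot would. Differing overall site means should not decide which sites are left out of the sensitivity analysis.

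The cost is SAP wording and a few lines of code, since both factors are known at randomisation. If the strata turn out not to be prognostic, the primary loses 0 to about 2.5 points of power and endpoint c about 1 point or less.

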### 3 ENDPOINT ANALYSIS

#### 3.1 Primary Endpoint

##### 3.1.1 Hypotheses

The primary endpoint is “Volume of aspirated cyst fluid as a function of estimated maximal volume based on pre-aspiration EUS measure of cyst diameter (s) (% aspiration of total estimated volume).”

Analysis Approach:

% aspiration of total estimated volume is calculated overall and for each arm (19 G Flex, 22 G, 19 G) and/or a combination of arms such as 19G Flex and 19G, for each and combined morphologic characteristics, and for no salvage subjects. If there is multilocular morphology, the primary endpoint is calculated for measurements of the largest locule.

Valid Data Sources:

- Procedure Form: sections “PCL Characteristics” and “Post-Aspiration Assessment”

Valid Data Points:

- Morphology: Unilocular (Pre-aspiration EUS measures)
  - Maximal diameter (long axis) (mm)
  - Perpendicular measurement (short axis) (mm)
- Morphology: Multilocular (Pre-aspiration EUS measures)
  - Measurements of the largest locule
    - Maximal diameter (long axis) of the largest locule (mm)
    - Perpendicular measurement (short axis) of largest locule (mm)
- Total volume of aspirate (Post-aspiration assessment)

Formula:

$$\% \text{ aspiration of total estimated volume} = \frac{A-B}{A} \times 100 \%$$

Volume is computed using the standard geometric formula  $\left(\frac{4}{3}\pi R^3\right)$  where R is half the long axis. The volume unit is in cc. “A” is calculated by the image during pre-procedure measurements. “B” is calculated by the image during post-procedure measurements.

Hypotheses:

$H_{0i}: \mu_i - \mu_0 \leq 0$  Versus  $H_{1i}: \mu_i - \mu_0 > 0$  for  $i=1, 2$ ;

where  $\mu_0$  is mean volume percentage of 22 G Arm,  
 $\mu_1$  is mean volume percentage of 19 G Flex Arm, and  
 $\mu_2$  is mean volume percentage of 19 G Arm.

Superiority by 10% or more is deemed clinically significant.

The multiple comparison Hochberg's step up method will be used.

The analysis population for the primary endpoint will be the Intent to Treat and Per-protocol analysis sets.

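### The confirmatory primary test ignores the number of locules, which is recorded before puncture and may be strongly prognostic; adjustment for it should be prespecified

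*SAP*

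**What the plan says.** - **Primary test.** SAP 3.1.3 states that the two-sample t "test statistic will be computed as follows": a difference of raw arm means over an unpooled standard error, referred to the standard normal. There is no covariate or stratum term. SAP 3.1.1 adds "The multiple comparison Hochberg's step up method will be used", for the two comparisons with 22 G. SAP 3.1.2 sets "One-sided Type I Error=0.05".
- **Locularity and size.** Protocol 8.3.1 has both assessed by EUS before FNA begins. Protocol 8.2.4 stratifies randomisation by centre and PCL location only.
- **Where they are used.** SAP 5.5 says "Multivariate analyses will be carried out to assess potential correlations between the primary endpoint and PCL location, PCL size, route of access", then lists needle used and number of locules; protocol 9.3 says the same. SAP 3.1.1 also has the endpoint calculated by morphology, and for multilocular cysts bases it on the largest locule. None of this feeds the Hochberg procedure.
- **The one locularity figure.** For one investigator, Figure 4 (protocol 9.1.1) gives "90% Unilocular cysts, 50% Multi-locular" cysts, blended to 80%, in the 19 G/19 G Flex column. The same investigator's 22 G entry is an undivided 80%.

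**The concern.** A strong predictor that is known before the needle enters, but left in the error term, widens the standard error of both primary comparisons. Randomisation does not balance locularity by design, so a chance excess of multilocular cysts in one arm passes straight into the confirmatory estimate. At stake is the probability of rejecting both nulls, which is how the protocol defines power for the primary endpoint. The model that does contain locularity cannot repair this, because it is exploratory and its treatment term is not stated to be the randomised arm.

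**Working it through.** **1. Reproducing the plan.** Inputs from SAP 3.1.2: means 67/77/77, SDs 15.29/4.67/4.67 and n = 25/25/50 for 22 G/19 G/19 G Flex, one-sided 0.05, Hochberg. Both nulls are rejected when both statistics exceed 1.645. Simulation with Welch t-tests gives conjunctive/global power 0.904/0.915; the SAP's normal reference gives 0.914/0.926. The stated figures are 0.901/0.912, so the calculation reproduces.

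**2. Same SDs at the enrolled size.** With 121/61/61, conjunctive power is 0.999. On the plan's inputs there is nothing to gain.

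**3. What those SDs are.** The protocol introduces Figure 4 with "The study investigators provided the following experience-based estimate of the primary endpoint", and its bootstrap yields "standard deviation of 15.29% for 22G, and a mean of 85.9% and standard deviation of 4.67% for 19G/19G Flex". The raw SDs of the six entries are 16.0 (22 G: 50, 70, 80, 90, 50, 65) and 4.9 (19 G: 80, 90, 80, 90, 90, 85). The planning SDs therefore describe disagreement between investigators about means, not variation between patients.

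**4. What the locularity figure implies.** From 90(1 − p) + 50p = 80, the multilocular share is p = 0.25. A 40-point gap then contributes variance 0.25 × 0.75 × 40² = 300, an SD of 17.3, which exceeds both 15.29 and 4.67. A 20-point gap contributes 75.

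**5. Power with and without adjustment.** Assumptions not in the documents: total patient SD of 25 or 30 in every arm, and 25% multilocular in every arm. Effect: 10 points, from "Superiority by 10% or more is deemed clinically significant". With arm variances v:

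- SE(Flex − 22 G) = √(v_Flex/121 + v_22/61)
- SE(19 G − 22 G) = √(v_19/61 + v_22/61)
- correlation = (v_22/61) / (product of the two SEs)
- power = P(both Z > 1.645), each Z having mean 10/SE

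At SD 30 unadjusted, v = 900: SEs 4.71 and 5.43, correlation 0.58, power 0.48. Adjusting for a 40-point gap in all arms, v = 900 − 300 = 600: SEs 3.85 and 4.44, power 0.66. With the gap in the 19 G arms only, v_22 stays at 900: SEs 4.44 and 4.96, power 0.56.

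| Scenario | SD 25 | SD 30 |
|---|---|---|
| Unadjusted | 0.64 | 0.48 |
| Adjusted, 40-point gap, all arms | 0.91 | 0.66 |
| Adjusted, 40-point gap, 19 G arms only | 0.77 | 0.56 |
| Adjusted, 20-point gap, all arms | 0.70 | 0.52 |

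The 19 G-only row treats the sample's locularity mix as fixed. Counting its sampling adds 300/243 = 1.23 to each squared SE and gives about 0.74 and 0.54.

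**6. A second parameterisation.** Here the gap is added to an assumed residual SD, and the trial is simulated at 121/61/61 with centred locularity, an arm-by-locularity term and robust standard errors (unadjusted → adjusted).

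| Residual SD, 22 G / 19 G arms | 40, all arms | 40, 19 G arms only | 20, all arms |
|---|---|---|---|
| 15.29 / 4.67 | 0.81 → 0.999 | 0.93 → 0.996 | 0.98 → 0.999 |
| 15.29 / 15.29 | 0.71 → 0.97 | 0.85 → 0.96 | 0.92 → 0.97 |
| 25 / 25 | 0.47 → 0.65 | 0.53 → 0.63 | 0.59 → 0.64 |

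The gain is about 6 to 26 points for a 40-point gap and 2 to 5 for a 20-point gap.

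**7. Chance imbalance.** With 61 per arm, one SD of imbalance shifts the 19 G − 22 G contrast by 40 × √(0.25 × 0.75 × 2/61) = 3.1 points (1.6 for a 20-point gap), against a 10-point target.

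**The case against.** The unadjusted test is valid. Chance imbalance is already allowed for in its type I error, and adjustment is a choice about efficiency. The primary endpoint needs 100 subjects by the plan's calculation, while 250 are enrolled because endpoint c needs 243. Even with an SD of 15.29 in every arm, conjunctive power at 121/61/61 is 0.97. The SAP also looks at locularity in the morphology breakdown and in section 5.5. All of this stands. It limits the size of the point but does not remove it, because the SDs behind the reassuring power are not patient-level and conflict with the locularity entry in the same table.

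Four stronger readings are tempting and are not supported:

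- *The protocol shows a 40-point gap.* It records one investigator's experience-based estimate for one needle column. No gap is given for 22 G, and the other five investigators give no split. Figure 4 does not say that the 50% refers to the largest locule, which is what the endpoint uses, so the gap could be smaller or absent on this endpoint.
- *Power is being thrown away.* That needs a patient SD well above the planned values. Figure 4 suggests one; the documents do not establish it.
- *Cyst size would add power too.* No figure links size to percentage aspirated, and pre-puncture diameter already defines the endpoint's denominator.
- *The operator picks the route of access knowing the needle.* No section says so. What can be said is that protocol 8.3.2 records route as part of the FNA procedure, after randomisation, so the assigned needle could influence it. Locularity is also recorded after randomisation, but it describes the cyst before the needle enters.

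**Conclusion.** The point holds as a worthwhile efficiency improvement and as protection against an understated SD. It is not an error that invalidates the primary test. If a 40-point gap applies in all arms and the patient SD is 25 to 30, the unadjusted test gives up 18 to 27 points of conjunctive power. If the gap is confined to the 19 G arms, the loss is 8 to 13 points, slightly less once sampling of the locularity mix is counted. With a 20-point gap in all arms it is 4 to 6 points. On the plan's own SDs it is nil. The patient SD, the 25% multilocular share in every arm and the 20-point gap are assumptions. In every scenario run with a locularity gap, the adjusted test had more power than the unadjusted one.

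**What to change.** - **SAP 3.1.3:** make the primary test a linear model of percentage aspiration on randomised arm, unilocular/multilocular and the randomisation stratum PCL location, with heteroscedasticity-robust standard errors. Centre locularity, and include an arm-by-locularity term if the gap may differ by needle, as Figure 4 leaves open. Feed the two one-sided p-values into Hochberg as planned. Keep the present unadjusted test as a sensitivity analysis.
- **Diameter:** pre-puncture maximal diameter may be added as a covariate, with no power gain claimed for it.
- **SAP 5.5:** in any model meant to give an adjusted treatment effect, use randomised arm rather than needle used, and leave out route of access.

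The cost is SAP wording and one model; locularity and location are already collected. The change must be written into the SAP before the final analysis, since protocol 9.3 labels changes to the plan and additional analyses as ad hoc.
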